4.4.1 Key/confirmatory secondary endpoint(s)

4.4.1.1 Definition of endpoint(s)

- Absolute change in eGFR values from baseline at Week 48 (using both Stage 1 and Stage 2 data), and Week 96 (using Stage 2 data only) during the placebo-controlled treatment period
- Time to reach the composite endpoint that includes $\geq 40\%$ reduction in eGFR, or kidney failure (defined by an eGFR ≤ 15 mL/min/1.73 m² at two consecutive visits or initiation of hemodialysis, or kidney transplant) during the placebo-controlled treatment period
- Percentage change from baseline in fatigue, as measured by the FACIT-F scales at Week 48 during the Stage 2 placebo-controlled treatment period, in the primary population
- Percentage of participants experiencing meaningful worsening in their fatigue, measured by the FACIT-F scales, at Week 48 during the Stage 2 placebo-controlled period, in the primary population.

The FACIT-F is a 40-item measure that assesses self-reported fatigue and its impact on daily activities and functions. The FACIT-Fatigue subscale will be used to measure fatigue in adult participants from Stage 2 of the study. The FACIT-F was designed to measure fatigue associated with anemia among cancer patients, but has been used widely across numerous therapeutic areas, including patients with kidney disease (4, 5). The FACIT-F includes 13 items that measure the severity of fatigue [REDACTED] and the impact of fatigue on functioning [REDACTED]. Patients rate their experiences over the “past 7 days” using a 0-4 verbal rating scale (“Not at all” to “Very Much”). The complete FACIT-F Fatigue subscale is included in Figure 1. The FACIT-F is scored as a sum of all 13 of the item responses; the scale range is from 0-52. After appropriate reverse scoring of 11 items, lower scores on the FACIT-F indicate greater levels of fatigue.

A pediatric version of the FACIT-F will be administered to patients 12-17 years old (6). The Pediatric FACIT-F includes 13 items that measure the amount of time that fatigue was experienced and impacted functioning. The Pediatric FACIT-F was developed for use with pediatric cancer patients but has also been used in other areas (7). Patients rate their experiences over the “past 7 days” using a 0-4 verbal rating scale (“None of the time” to “All of the time”). The Pediatric FACIT-F scale is included in Figure 2. As consistent with the adult version, the total score scale range is from 0-52.

4.4.1.2 Main analytical approach

Similar to the primary endpoint analysis, to control the overall Type 1 error rate at one sided 0.025, the secondary endpoints will also be analyzed for double blind placebo-controlled period of Stage 1 and Stage 2 data combined.

4.4.1.2.1 Analysis for absolute change in eGFR values from baseline at Weeks 48

Combined data from both Stage 1 and Stage 2 data during placebo-controlled period will be analyzed with a mixed effects model with repeated measures (MMRM) by treating time as a categorical variable. The model will include eGFR measurements from baseline to 48 weeks of double blind, placebo-controlled period as response variables, and it will include fix effects of treatment (lademirsen or placebo), screening eGFR stratification factor, age category (<18 versus ≥ 18 years old), screening SGLT inhibitor treatment (with versus without), time, and treatment-by-time interaction. Time will be treated as categorical variable. Due to the potential lack of convergency due to large number of visits, only data from Week 12, 24, 36, 40, 44 and 48 will be included in the model.

To model the within patient errors, an unstructured (UN) covariance structure will first be fitted, and if the model does not converge with both Hessian and the G matrix being positive definite, the model will be re-fitted using the covariance matrices of the following order specified by a decreasing number of covariance parameters until convergency is met:

- Heterogeneous Toeplitz (TOEPH)
- Heterogeneous First-order autoregressive (AR(1))
- Homogeneous Toeplitz (TOEP)
- AR(1)
- Heterogeneous compound symmetry (CSH)
- CS

The first covariance structure yielding convergence will be used in the analysis. When the unstructured covariance matrix is used, the Kenward -Roger approximation (DDFM=KR in SAS PROC MIXED) will be used to estimate the denominator degrees of freedom, otherwise, denominator degrees of freedom will be estimated using the between within method (DDFM=BW in SAS PROC MIXED).

4.4.1.2.2 Analysis for absolute change in eGFR values from baseline at Weeks 96

Since only Stage 2 has 96 weeks placebo-controlled treatment period, for the endpoint of absolute change in eGFR values from baseline at Week 96, only Stage 2 data during placebo-controlled period will be analyzed with a mixed effects model with repeated measures (MMRM) by treating time as a categorical variable. The model will include eGFR measurements from baseline to 96 weeks of the double blind, placebo-controlled period as response variables, and it will include fix effects of treatment (lademirsen or placebo), screening eGFR stratification factor, age

category (<18 versus \geq 18 years old), screening SGLT2 inhibitor treatment (versus those without), time, and treatment-by-time interaction. Time will be treated as categorical variable. The same variance-covariance matrix as specified in [Section 4.4.1.2.1](#) will be used. Due to the potential lack of convergency due to large number of visits, only data from Week 12, 24, 36, 48, 60, 72, 84, 88, 92, 96 will be included in the model.

4.4.1.2.3 *Analysis for time to reach Composite endpoint during the placebo-controlled treatment period*

Time to reach composite endpoint (as defined in [Section 4.4.1.1](#)) will be summarized by treatment group using Kaplan-Meier estimate. A stratified log rank test adjusting for screening eGFR stratification factor, SGLT2 inhibitor treatment at time of screening (with versus without), and age groups (<18 versus \geq 18 years old) will be used to compare between treatment groups for data from placebo-controlled period of Stages 1 and 2 combined. Subjects who have not reach composite endpoint will be censored at the last available day in double-blind period for subjects who entered into open label treatment and will be censored at the last available day in the study for subjects who discontinued study and did not enter open label treatment.

4.4.1.2.4 *Analysis for the patient reported outcomes*

For the percentage change in fatigue, as measured by Functional Assessment of Chronic Illness Therapy-Fatigue (FACIT-F) scales at Week 48 of placebo-controlled period, we will only have data from Stage 2. Therefore, Stage 2 data during placebo-controlled period will be analyzed with a mixed effects model with repeated measures (MMRM) by treating time as a categorical variable. The model will include all the data from placebo-controlled period up to Week 48 as response variables, and it will include fix effects of treatment (lademirsen or placebo), baseline value, screening eGFR stratification factor, age category (<18 versus \geq 18 years old), SGLT2 inhibitor treatment at screening (with versus those without), time, and treatment-by-time interaction. Time will be treated with categorical variable. The same variance-covariance matrix as specified in [Section 4.4.1.2.1](#) will be used.

Thresholds for meaningful within-patient improvement on the FACIT-F total score at Week 48 will be calculated using blinded data from the current study with methods described in PRO Psychometric Statistical Analysis Plan. The thresholds will be added to the SAP prior to the unblinding for the interim efficacy analyses (interim analysis 3).

For FACIT-F total score, a binary endpoint will also be derived. Subjects will be defined as meeting meaningful worsening criteria at week 48 if meet or exceed the meaningful change threshold at respective weeks. For patients who have missing data at Week 48, as a conservative approach, they will be considered as meeting meaningful worsening criteria for the specific week. The binary measure of meeting meaningful worsening criteria (yes vs no) at Week 48 will be analyzed with logistic regression including treatment, screening eGFR stratification factor, age category (<18 versus \geq 18 years old), screening SGLT2 inhibitor treatment (with versus without) as covariates. Number and % of responder, as well as odds ratio, 95% CI and p-value from the logistic regression model will be provided.

Cumulative distribution functions (CDFs) will be generated by treatment group for FACIT-F. The CDFs will show the cumulative percent of patients on the y-axis and percentage change from baseline to Week 48 on FACIT-F on the x-axis. The CDFs will allow a visual inspection of the cumulative proportion of patients in each treatment group who achieved various levels of percentage change on the FACIT-F at Week 48.

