7.2.1 Determination of sample size

An approximate 45 total subjects will be randomized in 2:1 ratio to lademirsen (SAR339375) versus placebo. The sample size will provide approximately 75% power to detect a reduced rate of decline of 5 mL/min/1.73 m²/year (~50% reduction) in eGFR annualized rate under lademirsen (SAR339375) treatment, in comparison to placebo.

Power calculations were based on simulations. The following model parameters were obtained from preliminary analysis of the ATHENA Natural History Study (OBS16374) data:

- Average linear decline in eGFR of 10 mL/min/1.73 m²/year in placebo arm
- Standard deviation (SD) for the residual error of eGFR of [REDACTED] mL/min/1.73 m² and SD for random effect of slope to be [REDACTED] mL/min/1.73 m²/year
- Mean and SD for intercept to be [REDACTED] mL/min/1.73 m² and [REDACTED] mL/min/1.73 m², respectively

In addition, power calculations were based on a success criterion defined in [Section 7.2.5](#) and a 10% dropout rate was assumed.

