7.2.5 Efficacy analysis

Estimated GFR will be calculated using the CKD-EPI creatinine equation as described by (32). For French subjects, see [Section 10.5.3](#).

Annualized rate of change in eGFR during the placebo-controlled treatment period will be compared between lademirsen (SAR339375) and placebo using a linear mixed effect model. ATHENA Natural History Study (OBS16374) data will be used as prior information supplementing the placebo arm, using a Bayesian approach.

The model will include eGFR measurements from baseline to Week 48 as response variables, and it will include fix effects of treatment (lademirsen [SAR339375] or placebo), screening eGFR stratification factor, time, and treatment-by-time interaction. In addition, it will include random intercept and random slope for time to account for the between subject variability. Time will be treated as continuous variable based on actual eGFR assessment date relative to the randomization date.

A prior distribution for the slope of the placebo group was determined based on the annualized rate of change in eGFR observed in a subgroup of subjects from ATHENA Natural History Study, who are considered as rapid progressors meeting renal function criteria similar to I 05 in [Section 3.2.1](#). The prior distribution assumes a normal distribution for the slope of eGFR in the placebo group, with a mean of -10 and standard deviation of 2.22. Non-informative priors will be used for other parameters in the model. Efficacy of lademirsen (SAR339375) will be based on the posterior probability that the slope of the lademirsen (SAR339375) group is greater than the slope of the placebo group. A posterior probability of at least 95% will be considered significant.

The primary estimand will be the difference in mean slope of eGFR estimated from baseline to Week 48 in ITT population, regardless of whether or not subjects completed the study period of 48 weeks.

Change and percent change from baseline in eGFR at Week 24 and 48 will be analyzed using mixed effects model with repeated measures (MMRM), based on eGFR measurements up to Week 48.

The number and proportion of subjects who reach ESRD or initiation of hemodialysis or renal transplantation will be summarized by treatment group. The proportion will be estimated based on

total subjects in ITT population, as well as the Kaplan-Meier estimate taking consideration of lost to follow-up during the study.

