2 SAMPLE SIZE DETERMINATION

This study has two stages as described in [Section 1.1](#). It also has three interim analyses planned as described in [Section 4.9](#).

- [REDACTED]
- [REDACTED]

With total sample size of 118 (43+75) subjects for the primary efficacy analyses, the study will provide approximately 92.6% (regardless of two interim futility analyses decision) power at either formal interim analysis for efficacy (3rd interim analysis) or final analysis to detect a reduced rate of decline of 5 mL/min/1.73 m²/year (~50% reduction) in eGFR annualized rate under lademirsen treatment, in comparison to placebo.

The power calculations were based on simulations of a frequentist random coefficient linear mixed effect model which is detailed in [Section 4.3.2](#). For the simulation, the following model parameters were obtained from analysis of the ATHENA Natural History Study (OBS16374) data:

- Average linear decline in eGFR of 10 mL/min/1.73 m²/year in placebo arm
- Standard deviation (SD) for the residual error of eGFR of [REDACTED] mL/min/1.73 m² and SD for random effect of slope to be [REDACTED] mL/min/1.73 m²/year
- Uniform enrollment of 1 years for 43 subjects from Stage 1, and uniform enrollment of additional 1.67 years for additional 75 subjects from Stage 2. Also at the time of interim efficacy analyses (3rd interim analysis), all 43 subjects at Stage 1 already completed the 48 weeks double blind treatment period.
- In addition, 10% annual dropout rate overall for both Stage 1 and Stage 2 subjects with exponential distribution for time to dropout was assumed.

[REDACTED]

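### The Stage 1 MMRM for change in eGFR leaves out continuous baseline eGFR and words its response ambiguously. The likely cost is a few percent of precision at Week 48, possibly nil.

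*SAP*

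**What the plan says.** SAP 4.4.1.1 defines the endpoint as a change: "Absolute change in eGFR values from baseline at Week 48 (using both Stage 1 and Stage 2 data". The heading of SAP 4.4.1.2.1 agrees, and so does Protocol 7.2.5: "Change and percent change from baseline in eGFR at Week 24 and 48 will be analyzed using mixed effects model with repeated measures (MMRM". The sentence in SAP 4.4.1.2.1 that names the response reads differently: "The model will include eGFR measurements from baseline to 48 weeks of double blind, placebo-controlled period as response variables". For reasons of convergence the same paragraph then states that "only data from Week 12, 24, 36, 40, 44 and 48 will be included in the model".

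The fixed effects listed there are treatment, screening eGFR stratum, age category, SGLT inhibitor use, time and treatment-by-time. SAP 4.4.1.2.4, which gives the MMRM for FACIT-F, lists one more term: "it will include fix effects of treatment (lademirsen or placebo), baseline value, screening eGFR stratification factor".

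Section 3 of the addendum reports no major change of statistical method. It limits the efficacy models to Stage 1, drops covariates that concern only Stage 2, and keeps absolute and percentage change in eGFR at Weeks 24 and 48. The model left for the final analysis has treatment, stratum, time and treatment-by-time.

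**The concern.** There are two separate gaps.

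- **The response is not fixed.** A model cannot take responses from baseline onward and also use only Weeks 12 to 48. Two programmers could follow the paragraph and fit change, or raw eGFR at the six visits.
- **Baseline enters only as a two-level stratum.** Within a stratum, a patient whose measured baseline happens to be high tends to show a larger fall, through measurement error alone. Adjusting for measured baseline removes that part of the variance and corrects chance imbalance within strata.

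Stage 1 has 43 participants randomized 2:1, and the addendum expects some not to reach Week 48, so precision is scarce. At stake is the width of a secondary interval.

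**Working it through.** **The plan's own figure.** Neither document gives an SD, standard error or power for this MMRM. The nearest stated figure is for the slope comparison: "The sample size will provide approximately 75% power to detect a reduced rate of decline" (Protocol 7.2.1). It cannot be reproduced forward, because the residual, slope and intercept SDs are blacked out. I therefore used it to limit which SDs are plausible.

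**Calibration to 75%.** Inputs are a placebo slope prior "with a mean of -10 and standard deviation of 2.22", a posterior threshold of 95%, a difference of 5 per year, and 30 versus 15 participants with 0-10% loss. Let s be the per-patient slope SD. In a normal approximation with 10% loss (27 versus 13.5) and s = 8.27:

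- placebo posterior variance = 1/(1/2.22² + 13.5/8.27²) = 2.498, and weight on the data = 0.493
- posterior SD of the difference = √(8.27²/27 + 2.498) = 2.243
- sampling SD of the posterior mean difference = √(8.27²/27 + 0.493² × 8.27²/13.5) = 1.940
- power = Φ((5 − 1.645 × 2.243)/1.940) = Φ(0.675) = 75%

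With no loss, s = 8.72. SAP 5.3 schedules eGFR at baseline, Weeks 2 and 4, then every 4 weeks. That is 14 values to Week 48, with Sxx = 1.235 yr², and s² = tau² + sg²/1.235 (tau = slope SD, sg = residual SD). For sg from 3 to 7, tau runs from 8.3 down to 5.4.

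**Within-stratum SD (si), assumed 7-9.** Screening eGFR is >35 to <90, split at 60. A uniform spread gives 25/√12 = 7.2 and 30/√12 = 8.7.

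**Formulas.** With complete data, zero intercept-slope correlation, T = 48/52.18 = 0.920 years and k = √(1/28.67 + 1/14.33) = 0.3235:

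- change, unadjusted: k√((tau·T)² + 2sg²)
- baseline-adjusted: k√((tau·T)² + 2sg² − sg⁴/(si² + sg²))
- raw eGFR, unadjusted: k√(si² + (tau·T)² + sg²)

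Here the covariance of change with baseline is −sg² at every visit, so one common baseline coefficient is enough.

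**Example** (sg 5, tau 6.94, si 8): (tau·T)² = 40.76. Change: 0.3235 × √90.76 = 3.08. Adjusted: 0.3235 × √(90.76 − 625/89) = 0.3235 × √83.74 = 2.96. The unadjusted SE is 4.1% larger.

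**Change as response, size of the unadjusted SE relative to the adjusted SE**

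| Setting | Range |
|---|---|
| Week 48, formula | +0.6% (2.824 v 2.807; sg 3, tau 8.29, si 9) to +11.8% (3.578 v 3.200; sg 7, tau 5.36, si 7); median 4.0% |
| Week 48, simulation | −0.6% to +10.0% |
| Week 24, formula | +1.4% to +14.4% |
| Week 24, simulation | +0.1% to +13.1% |
| Percent change, Week 48, simulation | −1.1% to +5.1% |
| Percent change, Week 24, simulation | −0.9% to +10.1% |
| Six-visit GLS, Week 48, none missing | +0.3% to +10.7% |
| Same, 20% lacking Week 48 | +0.2% to +9.2% |
| Same, 40% lacking Week 48 | +0.2% to +7.6% |

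The simulation used 43 patients, stratum in both models and 20,000 replicates at each of 12 calibrated points. A separate simulation with SDs not tied to the power figure gave −0.7% to +7.0% at Week 48.

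**Sensitivity.** An intercept-slope correlation of −0.3 moves the Week 48 formula range to 7-19%; +0.3 moves it to 0-7%. SAP section 2 gives a second figure, "the study will provide approximately 92.6% (regardless of two interim futility analyses decision) power", with 118 participants. Used as a rough further limit (one-sided 2.5%, interim ignored), it points to sg of about 5-7, where the range is 3.2-11.8%.

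**Raw eGFR as response, Week 48.** The formula gives 11.1-43.5% larger, or 11.1-31.5% for sg 5-7.

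**The case against.** **The plan means change.** The section heading, the endpoint definition, Protocol 7.2.5 and the addendum all say so. This stands. A reader might infer an 11-44% loss from the sentence that names raw measurements, but that figure belongs to the less likely reading and should carry little weight.

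**Baseline may be intended as a response row.** The primary slope model in SAP 4.3.2 uses similar wording and keeps the pre-dose value at year 0, so the visit list might only thin post-baseline visits. With free baseline means by arm and complete data, that model gives the same contrast as the change-score analysis. This is possible, though the visit list taken literally excludes it. The precision figures for change would still apply. The SAS code for the primary model is blacked out and may or may not settle the matter.

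**Week 48 will be incomplete.** Randomization ended by the end of December 2021 and final lock was planned for 4 November 2022, about 44 weeks later. The missing-data rows are therefore the more relevant ones, and they are lower.

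**The stratum is already in the model.** This is true. The figures above measure only what baseline adds beyond it, so the FACIT-F contrast shows uneven drafting and not an invalid eGFR model.

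**Adding a covariate now weakens prespecification.** This also stands. The addendum follows the futility interim and the decision to terminate, so the change has a cost beyond one parameter.

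**Conclusion.** The point holds as a minor one. The text omits continuous baseline eGFR and does not state the response consistently. If change is analyzed, the Week 48 standard error is probably a few percent larger than it need be: about 0-12%, median about 4%, possibly nil, and less if many participants lack Week 48. That range rests on assumed SDs calibrated to the stated 75% power, a within-stratum SD of 7-9 and zero intercept-slope correlation. It is not a result the documents establish.

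A reader might infer that the comparison is biased. It is not: randomization protects the contrast with or without the covariate. A reader might also infer that the main result is affected. The primary slope model keeps the baseline measurement at year 0 with a random intercept, so it is untouched. The endpoint here is secondary, with no multiplicity adjustment, in a study already stopped. The same wording for Week 96 in SAP 4.4.1.2.2 no longer matters, because no Stage 2 participants were enrolled.

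**What to change.** In section 3 of the addendum, state that the MMRM response is change from baseline in eGFR at Weeks 12, 24, 36, 40, 44 and 48, with percent change in a separate model of the same form. Add continuous baseline eGFR as a covariate and keep the screening eGFR stratum. Each model then serves both Week 24 and Week 48.

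The cost is one extra parameter with 43 participants, using a value already collected. Where residual SD is small relative to slope SD there may be no gain. Because the covariate would be added after the futility interim, record that it was fixed before final database lock, and report the SAP 2.0 model without baseline next to it.

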4.4.2 Sensitivity analysis for FACIT-F

Two sensitivity analyses to ensure that the treatment effect is similar across the adult and adolescent samples for FACIT-F were proposed.

- For the first sensitivity analysis: percentage change from baseline in FACIT-F at Week 48 will be analyzed separately for adult and pediatric.
- For the second sensitivity analysis: for percentage change from baseline in FACIT-F at Week 48, only items in the adult and pediatric measures that use common language [eg, “I feel tired,” “I feel weak (all over)”] will be used in calculating the total fatigue score. This will eliminate items that differentiate the 2 measures and, therefore yield a score that is based on a common assessment across the age groups.

4.4.3 Supportive secondary endpoint(s)

For the supportive secondary endpoints that are safety, the main analytical approaches are discussed in [Section 4.7](#). For the supportive secondary endpoints that are pharmacokinetic (PK), the main analytical approaches are discussed in [Section 4.8.1](#). For the supportive secondary endpoints that are immunogenicity, the main analytical approaches are discussed in [Section 4.8.2](#). For the supportive secondary endpoints that are biomarkers, the main analytical approaches are described in [Section 4.8.4](#).

